**Single Normal sampling procedure for Acceptable Quality Level (AQL) 0.010%**

| Number of Fields | Sample Size | Accept/Reject Criteria |
|------------------|-------------|------------------------|
| 2-8              | 2           | 0/1                    |
| 9-15             | 3           | 0/1                    |
| 16-25            | 5           | 0/1                    |
| 26-50            | 8           | 0/1                    |
| 51-90            | 13          | 0/1                    |
| 91-150           | 20          | 0/1                    |
| 151-280          | 32          | 0/1                    |
| 281-500          | 50          | 0/1                    |
| 501-1,200        | 80          | 0/1                    |
| 1,201-3,200      | 125         | 0/1                    |
| 3,201-10,000     | 200         | 0/1                    |
| 10,001-35,000    | 315         | 0/1                    |
| 35,001-150,000   | 500         | 0/1                    |
| 150,001-500,000  | 800         | 0/1                    |
| 500,001-up       | 1,250       | 0/1                    |

## 4.2 ANALYSIS SETS

The primary analysis will be based on the Intent-to-Treat (ITT) analysis set defined as all randomized subjects (based on study conduit group assignment).

The following rules will apply to the ITT analysis set:

- Subjects in whom the wrong conduit is implanted (e.g. an HAV implanted in a subject randomized to an ePTFE graft) will be analyzed within their randomized group rather than in their implanted group
- Subjects in whom no study conduit was implanted will be considered as if abandoned on Day 0 and included in their randomized group
- Subjects in whom the site (upper vs forearm) of implantation is different from the intended site will be analyzed based on the intended site.

The analysis will be repeated using the modified Intent-to-Treat (mITT) analysis set defined as all subjects in whom a study conduit has been implanted (based on actual conduit implanted and the actual site).

A secondary analysis will be conducted in a Per Protocol (PP) analysis set defined as all subjects in whom a study conduit has been implanted (based on actual conduit implanted) and in whom there were no major protocol deviations or data integrity concerns.

Major protocol deviations will be reviewed and verified at the time of determination, the time between the database soft lock and hard lock. Humacyte will identify major protocol deviation categories prior to the close of the database for the primary, second and final analysis. An overall major protocol deviation listing will be reviewed just prior to database lock for final analysis. Humacyte will approve all final major protocol deviation determinations. The protocol deviations SAS dataset will then be generated but will not be entered into the database.

Safety analysis will be conducted using the safety analysis set, which is defined as all subjects who receive study treatment, with the subject's treatment group based on the treatment that was received.

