10.2 Analysis Population

Efficacy

The primary analysis will be in the Intent-to-Treat (ITT) population with confirmatory analyses in the modified Intent-to-Treat (mITT) and Per Protocol (PP) populations.

The ITT population is defined as all randomized subjects (based on study conduit group assignment).

The mITT population is defined as all subjects in whom a study conduit has been implanted (based on actual conduit implanted).

The PP population is defined as all subjects in whom a study conduit has been implanted (based on actual conduit implanted) and in whom there were no major protocol deviations.

Safety

The safety analysis will be conducted using the safety population, which is defined as all subjects who receive study treatment, with the subject's treatment group based on the treatment that was received.

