11.11 Protocol Deviations

A protocol deviation is any noncompliance with the protocol or associated GCP requirements. The noncompliance may be either on the part of the participant, the investigator, or the study site staff. As a result of deviations, corrective actions are to be developed by the site and implemented promptly. Although in principle protocol deviations are not permitted, under emergency circumstances, deviations may proceed without prior approval of Humacyte and the IRB/IEC to protect the rights, safety, and well-being of human subjects.

All protocol deviations will be documented and reported by the CRO during the course of the study in the monitoring reports. All deviations will be reported to Humacyte who will agree on the necessary actions to be taken.

If required per their guidelines, reports about protocol deviations must be provided to the local IRB/IEC.

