## **4 GENERAL CONSIDERATIONS FOR DATA ANALYSIS**

Statistical analysis of data from this study will be the responsibility of CTI Clinical Trial & Consulting Services. Any change to the data analysis methods described in the protocol will require an amendment of this SAP only if it changes a principal feature of the protocol. Any other change to the data analysis methods that are described in the protocol, and the justification for making the change, will be described in the clinical study report. Additional exploratory analyses of the data will be conducted as deemed appropriate.

Summaries and analyses will be performed by CTI Clinical Trial & Consulting Services and/or by Humacyte. Validated results will be reviewed by statisticians and clinicians at Humacyte for approval. For both safety and efficacy analyses, all analyses will be performed by treatment group (HAV, ePTFE graft). Subject listings of all data from the case report forms (CRFs) as well as any derived variables will be presented.

All analyses will be implemented using SAS Version 9.2 or more recent version.

The analyses for this study will be performed as follows:

- The primary analysis will be performed after all subjects are at least 18 months post-implantation and have completed the 18-month visit or have been censored for death, kidney transplant or withdrawal.
- A second analysis will be performed after all subjects are at least 24 months (2 years) post-implantation and have completed the 24-month visit or have been censored for death, kidney transplant or withdrawal.

- A final analysis will be performed after all subjects with a patent conduit at 2 years (24 months) have completed 5 years (60 months) of follow-up after implantation, or until conduit abandonment, if earlier.
- Additional ad hoc analyses may be performed as needed after the 24 month analyses.
- Interim safety and efficacy data will be provided periodically to the DMC as per the DMC Charter.

A hard database lock will be required for the data included in the planned primary (18 month) and second (24 month) analyses. Additional soft database locks may occur to support DMC activities. A final hard lock will be required for the final analysis.

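### Per Protocol exclusions are set by the sponsor at each of three locks with no stated masking to arm or outcome, so the confirmatory PP analyses are open to arm- and outcome-dependent exclusion

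*SAP*

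**What the plan says.** **Who decides, and when.** SAP 4.2 states that "Humacyte will identify major protocol deviation categories prior to the close of the database for the primary, second and final analysis". On timing: "Major protocol deviations will be reviewed and verified at the time of determination, the time between the database soft lock and hard lock". On authority: "Humacyte will approve all final major protocol deviation determinations". A further overall listing is reviewed just before the final lock, and the deviations dataset is kept outside the database.

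**What excludes a subject.** The SAP's PP set holds implanted subjects "in whom there were no major protocol deviations or data integrity concerns". Protocol 10.2 says only "in whom there were no major protocol deviations". Neither document lists the major categories or defines a data-integrity concern. Protocol 11.11 is broad: "A protocol deviation is any noncompliance with the protocol or associated GCP requirements".

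**What PP is for.** Protocol 10.3.2 and SAP 6.1 make ITT primary, with mITT and PP repeats as confirmatory. SAP 6.1.1 keeps that role at 24 months. SAP 4.2 itself calls the PP analysis secondary.

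**What is withheld.** Cumulative event rates, overall and by arm, are kept from staff managing the study or subject care (Protocol 2.4.3.5; SAP 3.2). DMC results are not disclosed to the sponsor (SAP 4.1). After each planned analysis, however, "Validated results will be reviewed by statisticians and clinicians at Humacyte for approval" (SAP 4).

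**The concern.** In a non-inferiority trial the PP analysis is there to show that the ITT conclusion does not depend on deviations. It can do so only if exclusion is unrelated to arm and outcome. Here the categories are chosen, and each subject is classified, late: SAP 4.1 places locking after source verification and query resolution, so patency outcomes are essentially complete. Investigators and subjects are not blinded, and nothing says that a subject's arm or outcome is kept from the person ruling on that subject's deviation.

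The categories are then identified again for the second and final analyses, after the sponsor has reviewed the 18-month results. Nothing requires the same list or preserves earlier decisions. SAP 6.1.1 also re-analyses patency at 18 and 12 months as part of the 24-month work and provides for PP repeats, so the same subjects and the same period could be reported on a different PP set.

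**Working it through.** **1. Exposure at each lock (SAP 4, 4.1, 4.2, 3.2, 6.1.1)**

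| Lock | Subject-level arm and outcome masked? | Primary result known to the sponsor? | PP analysis exposed |
|---|---|---|---|
| 18 months | Not stated | No; aggregate rates and DMC results are withheld | 18-month confirmatory |
| 24 months | Not stated | Yes | 24-month, including the 18- and 12-month re-analyses |
| Final | Not stated | Yes | Any PP analysis at the final lock |

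**2. The plan's own figure.** The plan gives no figure for PP membership. Its power statement (Protocol 10.5) supplies the rates used below, so I checked it first.
- Margin: HR = ln(0.50)/ln(0.60) = 1.357. Assumed true HR = ln(0.66)/ln(0.60) = 0.813.
- With exponential times, 16 months of uniform accrual, 12 months of minimum follow-up and 20% per year death censoring (rate from SAP 6.1), about 158 events are expected.
- Power = Φ[(ln 1.357 − ln 0.813) × √(158/4) − 1.96] = 89.5%, in line with the stated 90%. The point does not depend on this.

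**3. Crude shift at the plan's HAV rate.** Inputs: 175 HAV subjects, 66% event-free at 12 months, no censoring.
- Event-free: 0.66 × 175 = 115.5. Failures: 59.5.
- Exclude 5 failed HAV subjects: 115.5/170 = 67.9%, up 1.9 points.
- Exclude 10: 115.5/165 = 70.0%, up 4.0 points.
- Exclude 10 at random: (115.5 − 6.6)/165 = 66.0%, no change.

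**4. Effect on the PP non-inferiority test.** Assumptions: 175 per arm, exponential times, every subject followed for 18 months, no other censoring, no stratification. The ePTFE rate is carried to 18 months as 0.60^1.5 = 46.5%. The HR margin is ln(0.3648)/ln(0.4648) = 1.316, and the true HR is set at that margin. Non-inferiority is declared if the upper 95% limit of the log rate ratio, with standard error √(1/d₁ + 1/d₂), is below ln 1.316. There were 20,000 simulated trials per case.

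| Subjects excluded | Failed HAV only | Same number of failures from each arm | Same number at random from each arm |
|---|---|---|---|
| 0 | 2.5% | 2.5% | 2.6% |
| 4 | 3.8% | 2.4% | 2.6% |
| 5 | 3.8% | 2.3% | 2.5% |
| 9 | 5.8% | 2.0% | 2.5% |
| 18 | 11.1% | 1.7% | 2.4% |

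Entries are the chance of wrongly showing non-inferiority in PP. The Monte Carlo standard error near 2.5% is √(0.025 × 0.975/20,000) = 0.1 points, so the first row's differences and the 4-versus-5 tie are noise. Inflation appears only when exclusion depends on both arm and outcome.

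**The case against.** A good deal can be said for the plan, and most of it stands.

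- **PP decides nothing.** ITT is primary, the fixed sequence runs in ITT, and no success rule refers to PP. The mITT set is also confirmatory and leaves no room for deviation judgements. This stands and caps the severity.
- **The primary result is not reachable later.** A reader might infer that sponsor decisions taken after the primary result could change it. They could not: the 18-month PP set is settled before that hard lock.
- **Eligibility is not singled out.** A reader might infer that the SAP reopens eligibility breaches at each lock. SAP 4.2 does not mention eligibility; it enters only through the general definition in Protocol 11.11. The Medical Monitor confirms eligibility before randomization (Protocol 5.2), which should limit such cases.
- **Silence is not evidence.** The documents do not say that the sponsor's reviewers see arm and outcome, and nothing shows that selective exclusion occurred. Deviations are documented by the CRO during the study (Protocol 11.11), and major ones are listed by subject (SAP 5.2), so exclusions could be audited.
- **The illustrations are worst cases.** They remove failures from one arm only, and the documents give no counts.

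What remains is that the SAP states a positive rule: sponsor choice of categories at three separate times and sponsor approval of every case. No stated safeguard acts at subject level. A later audit can expose a biased exclusion but does not prevent it.

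**Conclusion.** The point holds as a preventable weakness in the confirmatory PP analyses, and it should be fixed. The 18-month PP analysis is exposed through subject-level knowledge of arm and outcome. The 24-month and final ones are exposed through that and through knowledge of the primary result. The ITT primary analysis and its fixed sequence are untouched.

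The size is hypothetical. Excluding 5 or 10 failed HAV subjects alone moves the crude 12-month HAV rate by 1.9 or 4.0 points against the 10-point margin. Under the working's simulation assumptions, excluding 9 failed HAV subjects (9/175 = 5.1% of the arm) raises the chance of a false PP finding from 2.5% to 5.8%. Random exclusion, or equal exclusion of failures from both arms, gives no inflation.

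Separately, the SAP's data-integrity ground is absent from the protocol's PP definition. It is tempting to read that ground as meaning only the site named in SAP 6.3. The documents do not establish this: the revision tables place the edit to the PP definition one SAP version before section 6.3 was added.

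**What to change.** Amend SAP 4.2 as follows.

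1. **One list.** Set out the major-deviation categories once, including which inclusion and exclusion breaches count, before the primary-analysis lock, and use that list at 24 months and final. The current SAP already adds Month 24 analyses, so the 18-month lock may have passed; the documents do not say. If it has, carry that lock's list forward unchanged.
2. **Masked review.** Make determinations on listings with arm, implanted conduit and patency outcome removed where feasible. Have the programmer flag deviations that reveal the arm, such as a wrong conduit or a breach of the HAV storage or tunnelling requirements.
3. **Controlled additions.** Let later locks add newly discovered deviations, eligibility breaches included, only under the fixed list. Report every change in PP membership with its reason. Freezing eligibility exclusions outright at the primary lock would be worse, because it would keep in PP any subject found ineligible later.
4. **One PP definition.** Reconcile the data-integrity ground with Protocol 10.2 and apply it by the same masked review. Do not limit it to one site, since that would retain compromised data found elsewhere.

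The cost is SAP wording, alignment with the protocol and a masked listing; no new data are needed. The drawback is that masking stays incomplete for deviations that reveal the arm.

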## 4.3 ASSESSMENT WINDOWS

No analysis windows are planned for the study regarding data collected outside the protocol specified windows. All data will be included in the analysis based on the visit as it is recorded in the database.

#### 4.4 HANDLING OF DROPOUTS OR MISSING DATA

The following rules will be used to handle the data for subjects who either died or withdrew for any other reason (had kidney transplant, lost to follow-up, subject decision, etc.) prior to the time of the efficacy analyses and therefore do not have data up to the time of the analyses:

- For the primary analysis, subjects who have patent study conduit at the time of death, kidney transplant, voluntary withdrawal or withdrawal due to non-compliance will be censored at that timepoint
- For the primary analysis, subjects who are lost to follow-up with a patent conduit will be censored at their last visit when it was known that the study conduit was patent
- For the primary analysis subjects lost to follow up whose study conduit was not patent at the last completed visit will be treated as abandoned at the time of study conduit occlusion
- A secondary analysis will be conducted following the rules above, except that death will be included as an event in conduit patency survival curves
- For dialysis efficiency, the most recent available data prior to the study visits will be used for the analysis
- No imputation for histology assessments. Data from histology assessments will be presented as is

No substitution of missing data will be used in laboratory measurements, vital signs, physical examinations and subject and graft status. In case of partially missing adverse event start dates, the start dates will be imputed by comparing to the implantation date of study conduit so that the corresponding AEs will be made treatment-emergent whenever possible, unless the available partial date information clearly indicates that the event happened before implantation. The general rule of imputation is to assign the first day of a month for a missing day and the first month of a year for a missing month when applicable. For interventions, if the date of a procedure has a missing day, the first day of that month will be assigned for the missing day unless the partial date has the same year and month as the implantation date, in which case, the day of the implantation will be assigned. For a partially missing initial renal replacement therapy date, the last day of the month will be assigned for the missing day and no imputation will be performed if both month and day are missing.

Data points that appear to be spurious will be investigated, and queried for possible resolution. Data points that are not resolved through queries will be included in the statistical analysis of the data as well as the data listings. Statistical analysis may also be performed with such apparently spurious data excluded as a sensitivity analysis to determine the impact of that data on the study results.

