3.2 Secondary Objectives

3.2.1 Key Secondary Objectives:

Efficacy

To compare the Primary Patency of the HAV with that of the ePTFE graft.

Safety

To compare the rate of access-related infections for the HAV with that of the ePTFE graft.

3.2.2 Other Secondary Objectives:

Efficacy

1. To compare the rate of interventions needed to maintain/restore patency of the HAV with that of the ePTFE graft.
2. To compare the Primary Assisted Patency of the HAV with that of the ePTFE graft.
3. To describe the histopathological remodeling of samples from HAV and ePTFE grafts.
4. To compare the efficiency of dialysis with the HAV with that of the ePTFE graft in a subset of subjects.

Safety

1. To compare the safety and tolerability of the HAV with that of the ePTFE.
2. To compare the relative rates of true aneurysm and pseudo-aneurysm formation.

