4.2 Study Endpoints

4.2.1 Primary Endpoint

Time to loss of Secondary Patency from implantation

- Defined as 'the interval from the time of access placement until access abandonment', i.e., patent with or without interventions ([Sidawy 2002](#)).
- "Abandonment" defined as no remaining segment of the study conduit is incorporated into the vascular access circuit used for dialysis (conversely, if some portion of the study conduit is still being used for dialysis it is not considered abandoned).

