4.3 Duration of Study Participation

Each subject will be followed at study specific visits until he/she has completed 24 months of follow-up after implantation (irrespective of patency status). After 24 months, subjects with a patent study conduit will be followed (while the study conduit remains patent) for up to 5 years (60 months) post-implantation at routine study visits.

The expected duration of the clinical investigation is 76 months (initiation of enrollment through completion of data collection).

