8.5.1.8 Assessment of Adverse Events

The subject will be asked general questions about his/her health and for any conduit or dialysis problems since the previous visit. See [Section 9](#) for information regarding AE collection and data handling.

8.5.2 Evaluations and Procedures to be performed only at Specific Visits from Month 2 to Month 24

8.5.2.1 Duplex Ultrasound: Month 2, 3, 6, 12, 18 and 24

A duplex ultrasound will be performed to assess study conduit patency, diameter of the lumen mid-conduit, implant and anastomotic stenosis, volumetric flow rate, and to monitor for aneurysm development. The full length of the study conduit should be visualized with particular attention paid to any increase in diameter of the conduit that might indicate aneurysm formation.

8.5.2.2 Document Removal of CVC that was in place Pre-randomization: Month 2 and 3

Record the date and reason for removal of the CVC that was in place pre-randomization, if applicable.

8.5.2.3 Additional Data from Dialysis Unit: Month 3, 6, 12, 18 and 24

For a subset of subjects, the CRO will obtain, via data transfers from dialysis organizations, the following data obtained at a time closest but prior to the study visit (these data will be obtained from labs drawn at the discretion of the dialysis unit; where feasible and appropriate, these data will be obtained prior to study conduit implantation, too):

- $\text{spKt}/V_{\text{urea}}$ (to enable assessment of dialysis efficiency)
- Hemoglobin
- Erythropoiesis-stimulating agent (ESA) used and dose
- HbA1c (last value prior to study conduit implantation only)

8.5.2.4 PRA: Month 6, 12, 18 and 24

PRA samples will be drawn at Month 6, 12, 18, and 24. PRA samples should also be drawn prior to transplantation for any subjects who receive a transplant during the study.

8.5.2.5 Laboratory Data: Month 6, 12, 18 and 24

At Month 6, 12, 18 and 24, a blood sample will be collected for the following:

- Hematology: hemoglobin, hematocrit, RBC, WBC with differential, platelet count.
- Clinical chemistry: sodium, potassium, calcium, BUN or urea, creatinine, albumin, total bilirubin, ALT, AST, alkaline phosphatase, glucose (non-fasting)

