  - Rate of interventions defined as the number of interventions per subject per year while the conduit is patent (i.e. has not been abandoned). Results will be provided for Day 0 to Month 18 and overall (Day 0 to total follow-up period). Intervention rate for each 6-month interval will be reported.
  - The rate of interventions (number of interventions per 100 person-years) in the two arms will be compared using a Poisson regression model with treatment group and the surgical placement stratification variable as factors, if no overdispersion is present. Otherwise, a negative binomial regression will be used to adjust for overdispersion.
  - The number and rate of thrombectomies, angioplasties and revisions will be analyzed separately
- Interventions that failed to maintain/restore Secondary Patency. In the case when a delayed decision is made to abandon the study conduit (e.g. delayed and then failed thrombectomy), the date of abandonment is back dated to the initial recognition of the thrombosis. Any interventions performed after this date of abandonment will then be considered to have failed to maintain/restore Secondary Patency. Summaries for these interventions will include:
  - Proportion of subjects who had at least one failed intervention
  - Number of failed interventions per subject
  - Distribution of how many had 1, 2, 3 ... failed interventions

- Superiority analysis of the time to loss of Primary Assisted Patency using log-rank test at the 0.05 significance level and similar censoring rules discussed for the primary endpoint.
- Histology assessments of any conduits will be summarized descriptively. Summaries will include the following:
  - The proportion of subjects in whom a sample has been collected
  - The histological findings in each arm will be described and listed
- Dialysis efficiency as assessed by spKt/Vurea (obtained from dialysis unit for a subset of subjects) will be summarized descriptively. The most recent available data prior to the study visits will be used for the analysis.

All secondary endpoints will be summarized by treatment group using counts and percentages for the categorical variables, and n, mean, median, standard deviations, minimum and maximum for the continuous endpoints.

All secondary analyses will occur after all subjects complete at least 18 months post implantation.

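### The dialysis-efficiency rule does not require that the study conduit was in use, so values from a catheter or replacement access can count under the original arm

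*SAP*

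**What the plan says.** Protocol 3.2.2 lists as an other secondary objective: "To compare the efficiency of dialysis with the HAV with that of the ePTFE graft in a subset of subjects".

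The data come from the dialysis units. Under Protocol 8.5.2.3, for Months 3, 6, 12, 18 and 24, "the CRO will obtain, via data transfers from dialysis organizations, the following data obtained at a time closest but prior to the study visit". The laboratory draws are made at the unit's discretion, and Appendix 1 (note 9) says that sites take no part in the transfer. SAP 4.4 gives the analysis rule: "For dialysis efficiency, the most recent available data prior to the study visits will be used for the analysis". SAP 6.2 repeats it: "The most recent available data prior to the study visits will be used for the analysis". SAP 4.3 plans no analysis windows.

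Protocol 4.3 keeps every subject in follow-up to Month 24, patent conduit or not. Protocol 4.2.1 defines abandonment as the state in which "no remaining segment of the study conduit is incorporated into the vascular access circuit used for dialysis".

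SAP 6.2 summarizes the endpoint descriptively. Protocol 10.3.4 has a general line assigning a two-sample t-test to quantitative endpoints not otherwise covered.

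**The concern.** The objective concerns dialysis through a particular conduit, while the data rule concerns whatever dialysis the subject last had. By the protocol's own definition, a hemodialysis value obtained after abandonment cannot come from the study conduit, yet the rule tabulates it under the HAV or ePTFE heading. A value from a catheter still in use before first cannulation is treated in the same way. Without a look-back limit, an old value can also stand in for a later visit.

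Two distortions follow. A true difference between the conduits is diluted. And if other accesses dialyze better or worse than the study conduits, a difference in patency alone can show up as a difference in efficiency, because the off-conduit share can differ by arm.

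Elsewhere the SAP does restrict measures of this kind. Intervention rates count time while the conduit is patent (6.2). Exposure to a conduit used for hemodialysis runs from first cannulation to abandonment (7.1). One infection rate is censored at abandonment, and pseudo-aneurysm rates use time since first cannulation (7.2). No reason is given for treating dialysis efficiency differently.

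**Working it through.** **Inputs.** 12-month event-free rates for Secondary Patency: ePTFE 60%, HAV 66% (non-inferiority case) or 76% (superiority case), from Protocol 10.5. Phase 2 HAV 89% against 50% to 60% for synthetic grafts, from Protocol 2.4.3.3. Annual death rate about 20%, from SAP 6.1.

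**The plan's own figures.** The documents give no figure for the share of spKt/Vurea values obtained through the conduit. The planning rates come with stated powers of 90% for N = 350. I checked these with power = Φ(√(D/4)·|Δ log HR| − 1.96), where D is the number of events.
- Non-inferiority: margin HR = ln 0.50/ln 0.60 = 1.357; true HR = ln 0.66/ln 0.60 = 0.813; Δ = 0.512. With 16 months of accrual plus 12 months of follow-up, D = 185 and power is 93.6%. With 20% annual death censoring, D = 158 and power is 89.5%.
- Superiority: log HR = ln(ln 0.76/ln 0.60) = −0.621. With a fixed 12 months, D = 112 and power is 90.8%.

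Both stated powers can be approximated, but under different follow-up assumptions: non-inferiority with a fixed 12 months gives 82.9%, and superiority with 16 + 12 months gives 97.7%. The check supports the rates as planning inputs. It does not establish the shape of the hazard after 12 months.

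**Share abandoned, constant hazard.** Share = 1 − S12^(t/12), t in months; pooled 1:1.

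| Month | ePTFE (60%) | HAV (66%) | HAV (76%) | Pooled (66%) | Pooled (76%) |
|---|---|---|---|---|---|
| 3 | 12.0% | 9.9% | 6.6% | 10.9% | 9.3% |
| 6 | 22.5% | 18.8% | 12.8% | 20.6% | 17.7% |
| 12 | 40.0% | 34.0% | 24.0% | 37.0% | 32.0% |
| 18 | 53.5% | 46.4% | 33.7% | 50.0% | 43.6% |
| 24 | 64.0% | 56.4% | 42.2% | 60.2% | 53.1% |

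For example, at Month 24: ePTFE 1 − 0.60² = 0.640; HAV 1 − 0.66² = 0.564 or 1 − 0.76² = 0.422.

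**Sensitivity at Month 24.**
- Phase 2 HAV rate: 1 − 0.89² = 20.8%. Pooled with ePTFE at 60%: (64.0 + 20.8)/2 = 42.4%. With ePTFE at 50%: (75.0 + 20.8)/2 = 47.9%.
- Weibull, share = 1 − S12^(t^k), t in years, shape k from 0.5 to 1.2 (assumed range): pooled 47.9-65.3% (HAV 66%) and 41.8-57.9% (HAV 76%). The pooled share falls below half for k under about 0.59 and 0.87 respectively.
- Constant hazard, ePTFE 60%: the pooled share is below half once the HAV 12-month rate exceeds √(1 − 0.36) = 80%.

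**Effect on the contrast at Month 24, in units of an unknown difference d.** If HAV sessions exceed both ePTFE and all other accesses by d, the observed contrast is S_HAV·d: 0.436d (66%) or 0.578d (76%). If the two conduits are identical and other accesses are lower by d, a spurious HAV advantage of (S_HAV − S_ePTFE)·d appears: (0.436 − 0.360)d = 0.076d, or (0.578 − 0.360)d = 0.218d. The documents give no value for d.

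**What the shares leave out.** They treat death, transplant and withdrawal as independent of abandonment, the subset as representative, and the latest value as reflecting access status at the visit. Catheter use with a patent conduit would raise the off-conduit share. Higher mortality on catheters, or a latest value that predates a recent abandonment, would lower it.

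**The case against.** The endpoint carries little weight. It is an other secondary endpoint in an unspecified subset, outside the fixed testing sequence, and the SAP only describes it. The t-test is a generic protocol line that the SAP does not apply here. A summary by assigned arm regardless of patency is also a coherent treatment-policy description. Restricting to conduits still in use conditions on a post-randomization outcome: at Month 24, under the planning rates and a constant hazard, about 36% of ePTFE and 44-58% of HAV conduits would remain, so survivors would be compared. All of this stands. It limits the importance and shapes the fix, but does not make an all-access table an answer to an objective worded as efficiency with each conduit.

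Stronger readings that a reader might infer are not supported:
- *That most Month 24 values must be off-conduit.* This needs the planning rates and a roughly constant hazard. It fails in the HAV arm at the 76% rate, and in the pooled data at the Phase 2 rate. Protocol 2.4.3.2 describes very early technical and thrombotic failures, so a constant hazard cannot be presumed.
- *That Month 3 is dominated by values from before conduit use.* Pre-implant values are transferred in addition to the visit values, and a subject not yet on dialysis would ordinarily have no value. Cannulation from Day 28 leaves about 7 to 11 weeks before a Month 3 visit (±14 days). Catheter values at Month 3 are possible, since removal of earlier catheters is documented at Months 2 and 3, but their number cannot be estimated.
- *That the problem would be invisible.* Sites record alternate routes and their duration at each postoperative visit, and SAP 8 lists dialysis and catheter data. What is missing is a rule linking these records to the spKt/Vurea value.

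**Conclusion.** The point holds as a mismatch between objective and data rule. Neither document ties spKt/Vurea to use of the study conduit or sets an oldest allowed date, and follow-up past abandonment lets off-conduit values count under the original arm. The sturdier part is that this contamination can differ by arm: 64% against 42-56% of conduits abandoned by Month 24 under the planning rates and a constant hazard. The pooled 53-60% is conditional and can fall below half. At Months 3 to 12, abandoned conduits are a minority (9-37% pooled). The size of any distortion in spKt/Vurea is unknown, because the documents give no difference between accesses. The primary analysis, its power and the fixed sequence are unaffected. Importance is minor to moderate.

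**What to change.** In SAP 4.4 and 6.2:

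1. Set a look-back limit for each visit, for example no earlier than the previous scheduled visit.
2. Flag each value as on-conduit (after first cannulation, before the abandonment date, and no catheter or other route recorded as in use) or as off-conduit/unknown.
3. Present the on-conduit values as the summary that addresses the objective, with the number contributing per arm and visit. Place it next to the all-access summary by randomized arm.
4. Label the on-conduit comparison as one of surviving conduits, not protected by randomization.

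The cost is SAP wording and one derivation from data already collected: first cannulation, abandonment date, and the hemodialysis and catheter records. There are two downsides. Late on-conduit values will be fewer and will come from surviving conduits. And the route may have to be inferred from visit-level records rather than known for each session, which is why the flag needs an unknown category. Keeping both summaries means that no information is lost.
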